6.5.2.4 Survival

Perioperative Mortality: The distribution of vital status at 30 days post-surgery will be presented for each randomization arm and compared using chi-squared tests.

Mortality at 2 and 5 years post-randomization: Differences in the rate of mortality between randomization groups over the first 24 months and the planned 60 months of post-randomization follow-up will be assessed using Cox proportional hazards regression.

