Sample Size	400 patients provides 90% power to detect a decrease in “failure” from 25% without tricuspid valve repair to 12% in patients with repair.
Duration	60 months following randomization
1° Endpoints	
Composite of death, reoperation for TR, or progression of TR from baseline by two grades or the presence of severe TR at 24 months 
Degree of TV regurgitation will be categorized according to American Society of Echocardiography guidelines as none/trace/mild/moderate/severe

2° Endpoints	
Clinical and Functional Outcomes
 
Composite of major adverse cardiac and cerebrovascular events (MACCE), including stroke, death, and serious heart failure eventsNYHA classification and diuretic requirementsSix-minute walk test (6MWT)Gait Speed Test for Frailty 
Echocardiography
 
Degree of TR at index hospital dischargeDegree of TR at 12 and 24 monthsRight ventricular size at 12 and 24 monthsRight ventricular function [normal, mildly impaired, moderately impaired, severely impaired, peak tricuspid annular velocity, tricuspid annular plane systolic excursion (TAPSE), right ventricular fractional area change (RVFAC)] at 12 and 24 monthsPulmonary artery pressure at 12 and 24 monthsRight ventricular volume at 12 and 24 months 
Quality of Life
 
SF-12Kansas City Cardiomyopathy Questionnaire (KCCQ)EuroQoL (EQ-5D)

	
Survival
 
• Perioperative mortality (greater in-hospital or 30 day mortality)• Mortality 
Serious Adverse Events
 
• Frequency of serious adverse events (SAEs)• Atrioventricular (AV)-Block requiring pacemaker implantation• New-onset atrial fibrillation 
Hospitalizations
 
• Index hospitalization length of stay (LOS) and intensive care unit (ICU) days• All-cause readmissions, and readmissions for heart failure and TR reoperations 
Economic Outcomes
 
• Cost• Cost-effectiveness
Selected Inclusion Criteria	
1. Age \geq 18 years2. Undergoing MVS for degenerative MR3. (a) moderate TR as determined by echocardiography, or (b) none/trace or mild TR and tricuspid annular dimension \geq 40 mm

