- RV function (normal, mildly impaired, moderately impaired, severely impaired, peak tricuspid annular velocity, TAPSE, RVFAC) at 12 and 24 months
- Pulmonary artery pressure at 12 and 24 months
- RV volume at 12 and 24 months

Quality of Life

- SF-12
- KCCQ
- EQ-5D

Survival

- Perioperative mortality (greater in-hospital or 30-day mortality)
- Mortality

Serious Adverse Events

- Frequency of SAEs
- AV-Block requiring pacemaker implantation
- New-onset atrial fibrillation

Hospitalizations

- Index hospitalization LOS and ICU days
- All-cause readmissions and readmissions for heart failure and TR re-operation

Economic Outcomes

- Cost
- Cost-effectiveness

STUDY DESIGN

This is a multi-center randomized clinical trial. The trial will be conducted in highly experienced clinical centers participating in the NIH/CIHR supported Cardiothoracic Surgical Trials Network (CTSNet) and the Deutsches Zentrum für Herz- Kreislauf-Forschung (DZHK) supported German Society for Thoracic and Cardiovascular Surgery (DGTHG). The estimated enrollment period is 24 months (n = 400), and all patients will be followed for 60 months post-randomization. Endpoints will be measured at 30 days, 6, 12, 18, and 24 months. Survival will continue to be measured after the 24-month visit via vital sign checks at 36, 48 and 60 months.

RANDOMIZATION

Patients will be randomly assigned (1:1) to MVS + TV annuloplasty or MVS alone. Patient randomization will be stratified by TR severity and by clinical center. The randomization procedure will be performed intra-operatively, following **the placement of the TEE probe and after visualization and confirmation of cardiac anatomy eligibility**, in order to minimize the likelihood of enrolling patients in the study with

unexpected surgical contra-indications to TV repair. Randomization will be performed centrally through a Web-based data collection system that automates the delivery of the randomization assignments. The treatment assignment will be viewed by the site coordinator electronically, in a secure fashion, and electronic verification of the treatment assignment will be required before proceeding with the treatment intervention. From that point on, primary efficacy will be analyzed by intention-to-treat; that is, the patients will be grouped by their assignment at randomization whether or not they actually received the treatment to which they were assigned.

MASKING

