- 6 (± 30 days), 12 (± 30 days), 18 (± 30 days) and 24 months (± 60 days) post-randomization

²Needs to be manually bent into nonplanar shape similar to other commercially available annuloplasty rings

- 36, 48 and 60 months vital status check (± 60 days)

For patients who are unable to return to the clinical site for the *6- and 12-month* assessments because of extreme geographic distance, the clinical coordinator will obtain the required data from a remote clinical site outside of the CTSN sites. The remote clinical site *must* be identified in advance of discharge from the index hospitalization. All efforts must be made to acquire all follow-up at the CTSN clinical site. *All 24-month (Primary Endpoint) assessments must be performed in accordance with the protocol defined data collection whether the visit is conducted at a CTSN clinical site or remotely.* The 36, 48 and 60 month vital status checks may be conducted via telephone or via a search of medical records.

Surgical Procedures

Initial surgical intervention and event driven

The initial surgical procedure (MV surgery \pm TV repair) will be reported on the initial surgical Procedure form and all subsequent operations must be reported on the follow up surgical procedure form within 48 hours of the knowledge of the event. If the operation is to address a complication, the coordinator must also complete an AE report.

Initial Surgical Procedure

Routine information will be collected on the standard surgical procedure, the MV procedure, TV procedure and any concomitant procedures.

Follow-up Surgical Procedure

Information about any surgical procedure(s) performed following the initial surgical procedure and during the follow-up period through 24 months post-randomization will be collected on this form.

Hospitalizations

Index hospitalization

For all patients, the index (baseline) hospitalization must be reported on the Hospitalization form. This form collects limited information about LOS, days in ICU, and disposition at time of discharge (home, skilled nursing facility, rehabilitation facility, death).

Medications

At 30 days (-7 days, +35 days), 6 (± 30 days), 12 (± 30 days), and 24 months (± 60 days) post randomization and event driven

All cardiovascular medications will be recorded at each study visit, and also as indicated at the time of associated AEs.

Physical Examination

At 30 days (-7 days, +35 days), 6 (± 30 days), 12 (± 30 days), and 24 months (± 60 days) post randomization

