We propose considering increasing sample size should the observed primary endpoint event rate among patients randomized to no repair of the TV be appreciably less than the assumed rate of 25%. The planned sample size of 400 patients has been determined to ensure that power is at least 90% to detect a 52% relative reduction of “failure” for patients randomized to tricuspid repair compared to no repair. Should the “failure” rate among controls be 20%, 400 patients provides approximately 83% power to detect a 52% relative reduction; for a 15% “failure” rate among controls there is approximately 70% power to detect a 52% relative reduction. Therefore, we suggest that the primary endpoint event rate be examined in control patients, using the same analysis set to be used for the interim analysis, and that the sample size be increased by up to 100 additional patients in order to maintain 80% power under the original alternative hypothesis for control rates as low as 15%. If no interim analysis is conducted or accrual is complete at the time of the first interim analysis, the sample size re-estimation will not be considered.

Assessment of Balance of the Randomization

The success of the randomization procedure in balancing important covariates between randomization groups will be assessed at the interim analysis and at the final analysis. Continuous measures will be compared using t-tests, while chi-squared tests will be used to compare categorical variables. As 400 patients will be randomized, no substantial imbalances are expected. However, should any covariate differ significantly between treatment groups at the 0.01 level, and be substantively large, we will adjust for those covariates in a secondary analysis of the primary endpoint.

Additional analysis of the primary endpoint

A subgroup analysis of the primary endpoint will be performed with subgroups defined by whether or not patients received a CABG procedure during the initial surgery. This analysis will be performed in the same manner as that described for the primary analysis.

Analyses of Secondary Endpoints

Individual components of the primary endpoint

Mortality: Differences in the rate of mortality between randomization groups over the first 24 months and the planned 60 months of follow-up will be assessed using Cox proportional hazards regression.

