5.2.4 Survival

- Perioperative mortality (in-hospital or 30-day mortality)
- Mortality through 24 months post-randomization
- Mortality through 60 months post-randomization

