6. STATISTICAL METHODOLOGY

6.1 General Principles

Study day will be calculated from the reference start date, and will be used to show the study days of assessments and events. Reference start date is defined as the date of randomization unless otherwise specified. In analyses of index length of stay, index ICU days, peri-operative (30 day) mortality, and peri-operative (30 day) readmissions the reference date is

the date of surgery. In the situation where the event date is partial or missing, study day, and any corresponding durations are to appear partial or missing in listings. If a missing event date, such as a discharge date for a hospital readmission, is necessary to calculate patient-time at risk, the missing event date will be imputed using the median length observed for similar events.

Continuous variables will be summarized using the following descriptive statistics: number of non-missing values, means, standard deviations, medians, interquartile range, maximum, and minimum. Categorical variables will be summarized using number of non-missing values, counts and percentages.

Rates of events will be calculated as the ratio of the total number of events recorded divided by the total patient-time. Total patient-time will be calculated by summing the time (in study time units, e.g., days, months or years) that patients were at risk for a specific event from the reference time point until either study exit or the end of the time period of interest. Rates and 95% confidence intervals will be reported.

Time-to-event variables will be summarized using the Kaplan-Meier method or, in the presence of competing risk, the Gray method (Gray, 1988).

For any variable measured at multiple points in time, change from baseline will be calculated as the difference between the value of the variable at a specific point in time (e.g. 1 year) minus the baseline value. Relative change from baseline will be calculated as the value of a parameter at a specific point in time minus the baseline value of the parameter divided by the baseline value of the parameter. Percent change will be calculated as the relative change multiplied by 100.

All hypothesis testing will be conducted at the 0.05 two-sided significance level unless otherwise specified. P-values will be rounded to three decimal places. P-values less than 0.001 will be reported as <0.001 in tables. P-values greater than 0.999 will be reported as >0.999.

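### Perioperative mortality is defined with an in-hospital component, but the SAP analyses only 30-day vital status, so an index-stay death after day 30 would count as a non-event

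*SAP*

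**What the plan says.** **Definition.** SAP 5.2.4 (Survival) lists the endpoint as "Perioperative mortality (in-hospital or 30-day mortality", with a closing parenthesis. The protocol's Endpoints section has "Perioperative mortality (greater in-hospital or 30-day mortality", and its Abstract has "Perioperative mortality (greater in-hospital or 30 day mortality". All three name an in-hospital component.

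**Analysis.** SAP 6.5.2.4, in its entry for perioperative mortality, specifies: "The distribution of vital status at 30 days post-surgery will be presented for each randomization arm", with the arms compared by chi-squared test. SAP 6.1 (General Principles), in setting time origins, says that for "peri-operative (30 day) mortality, and peri-operative (30 day) readmissions the reference date is" the date of surgery. The protocol's Analytical Plan has no separate perioperative analysis. Its mortality entry covers differences "over the first 24 months and the planned 60 months of follow-up will be assessed using Cox proportional hazards regression".

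**Data.** The protocol's index hospitalization form records "disposition at time of discharge (home, skilled nursing facility, rehabilitation facility, death", and its Mortality form records the date of death.

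**The concern.** The endpoint list and the analysis rule do not describe the same set of deaths. A programmer who follows SAP 6.5.2.4 and 6.1 would produce 30-day mortality and report it under a name that the SAP and protocol define more broadly.

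The trial's stated objective covers safety as well as efficacy, and the protocol's Rationale records the view that the risk of an added procedure may outweigh its benefit. Perioperative mortality is the listed survival endpoint closest to that question. The deaths left out are those that end an index stay of more than 30 days. The error can run in one direction only: it can omit deaths that meet the definition but cannot add any.

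**Working it through.** The plan states no rate, count or power for this endpoint, so there is no figure to reproduce. The check is a comparison of texts, followed by an illustration of size.

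**1. Definition against rule.** Take three patients who die after surgery.

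| Death | SAP 5.2.4: in hospital or by day 30 | SAP 6.5.2.4: vital status at day 30 |
|---|---|---|
| Day 12, index stay | event | dead |
| Day 25, after discharge | event | dead |
| Day 40, still in index stay | event | **alive** |

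Only the third differs. No other section of the SAP or protocol adds such a death to this comparison.

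**2. The protocol's word 'greater'.** It has two possible readings.
- The longer window for each patient. A death is then an event if it occurs by the later of day 30 and index discharge. This is the same set as in-hospital or by day 30, and the day-40 death is an event.
- The larger of two rates, in-hospital and 30-day. The analysis then needs both rates, and SAP 6.5.2.4 supplies only one.

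Neither reading is met by 30-day status alone.

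**3. Possible size.** Inputs:
- 400 patients allocated 1:1, so 200 per arm (SAP 6.5.1.1).
- p, perioperative mortality under the full definition: assumed, 1%, 2% or 4%.
- s, the share of those deaths that fall in hospital after day 30: assumed, 5%, 10% or 25%.

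Formulas:
- Missed deaths per arm = 200 × p × s
- Reported rate = p × (1 − s)
- Chance of at least one missed death in the trial = 1 − (1 − p × s)^400

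| p | s | Missed per arm | Reported rate | Chance of at least one missed in 400 |
|---|---|---|---|---|
| 1% | 5% | 0.1 | 0.95% | 18% |
| 1% | 10% | 0.2 | 0.90% | 33% |
| 1% | 25% | 0.5 | 0.75% | 63% |
| 2% | 5% | 0.2 | 1.90% | 33% |
| 2% | 10% | 0.4 | 1.80% | 55% |
| 2% | 25% | 1.0 | 1.50% | 87% |
| 4% | 5% | 0.4 | 3.80% | 55% |
| 4% | 10% | 0.8 | 3.60% | 80% |
| 4% | 25% | 2.0 | 3.00% | 98% |

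For example, p = 2% and s = 10% give 200 × 0.02 × 0.10 = 0.4 missed per arm, and 1 − (0.998)^400 = 0.55.

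**4. Where the omitted deaths still count.** Death from any cause is a component of the primary composite (SAP 6.5.1) and of MACCE over 24 months (SAP 6.5.2.1). It is also the event in the 24- and 60-month Cox analyses (SAP 6.5.2.4).

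**The case against.** The strongest reply is that the SAP uses 30 days in both places where it puts the endpoint into operation, 6.1 and 6.5.2.4. That could be a deliberate 30-day definition, with loose wording in 5.2.4. The intent may indeed have been 30 days, but the contradiction remains. The SAP's own endpoint list and two places in the protocol say otherwise, and nothing states that the in-hospital part was dropped. Renaming the endpoint as 30-day mortality would restore consistency, but only by removing a component that the protocol specifies. The reply does show that editing 6.5.2.4 alone would leave 6.1 in conflict.

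The reply is also right that the consequence is limited. The comparison is one item in a long secondary list, and the documents give no power for it. A reader might take it for the trial's main early-safety comparison. The documents do not call it that: the secondary outcome that the protocol marks as of particular interest is MACCE, and adverse events, length of stay and ICU days are compared as well.

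A reader might also imagine both missed deaths in one arm, say 7 v 3 reported as 5 v 3. That is a worst case built on invented counts. With 200 per arm, the uncorrected chi-squared statistics are 400 × (7×197 − 3×193)² / (200×200×10×390) = 1.64 (p about 0.20) and 400 × (5×197 − 3×195)² / (200×200×8×392) = 0.51 (p about 0.475). Neither count would show a significant difference.

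**Conclusion.** The inconsistency is real, and the analysis rule as written can misclassify patients on a pre-specified secondary safety endpoint. What the documents support is that the comparison could undercount perioperative deaths if any index-stay death occurs after day 30. They do not support saying that it does so, because they give neither a perioperative mortality rate nor the timing of deaths. Over the assumed ranges the expected loss is 0.1 to 2 deaths per arm, and at the low end there is an 18% chance of even one such death in the whole trial.

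Two further inferences should be resisted. The deaths are not lost to the trial, since the primary composite and the main mortality analyses are unaffected. SAP 5.2.4 does not itself say that the longer window applies. That is one reading of the protocol's word 'greater', and the SAP should settle it.

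**What to change.** Three short edits to the SAP:

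- **6.5.2.4:** analyse a binary indicator of death within 30 days of surgery or before discharge from the index hospitalization, whichever is later. Show 30-day vital status separately if wanted.
- **6.1:** replace the 30-day label for perioperative mortality with the same definition, keeping the date of surgery as origin.
- **5.2.4:** state that the protocol's 'greater' means the longer of the two windows for each patient.

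No new data are needed, because discharge disposition including death and the date of death are already on the case report forms. The SAP's statement of purpose allows revisions before data lock and the primary analysis. The cost is a few lines of text and one derived variable.

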6.5.2.5 Serious Adverse Events

Differences in the rate of individual serious AEs, AV-Block requiring pacemaker implantation, and new-onset atrial fibrillation within 24 months post-randomization will be compared between randomization groups using Poisson regression. Ninety-five percent confidence intervals for the rate ratios for individual AEs for treatment with MVS and TV annuloplasty versus MVS alone will be computed.

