Neither patients nor investigators will be blinded to treatment assignment due to the nature of the treatment intervention. Investigators will, however, be blinded to all data from other clinical sites, except serious unexpected AEs that are possibly or probably related to the investigational procedure for IRB/REB/EC reporting purposes. All echocardiograms will be analyzed by echocardiography core laboratory (Echo Core Lab) personnel who will be blinded to clinical outcomes. Adverse events (AEs) will be adjudicated by an Event Adjudication Committee (EAC) and trial oversight will be provided by an independent Data and Safety Monitoring Board (DSMB).

STUDY POPULATION

The patient population for this trial consists of adult patients undergoing MVS via full or minimal-access sternotomy or right thoracotomy for degenerative MV disease using legally marketed devices. Specific inclusion and exclusion criteria are listed below. All patients who meet the eligibility criteria may be included in the study regardless of gender, race, or ethnicity.

Inclusion Criteria

1. Undergoing MVS for degenerative MR¹ with
 - (a) Moderate TR as determined by transthoracic 2D echocardiography, or
 - (b) Tricuspid annular dimension ≥ 40 mm (index: $\geq 21\text{mm}/\text{M}^2 \text{ BSA}$) and none/trace or mild TR, determined by echocardiography.
2. Age ≥ 18 years
3. Able to sign Informed Consent and Release of Medical Information forms

Exclusion Criteria

1. Functional MR

¹ “Degenerative mitral valve disease refers to a spectrum of conditions in which morphologic changes in the connective tissues of the mitral valve cause structural lesions . . . , such as chordal elongation, chordal rupture, leaflet tissue expansion, and annular dilation typically resulting in mitral regurgitation due to leaflet prolapse.” This definition excludes rheumatic heart disease. (Anyangwe AC, Adams DH. (2007) Etiological classification of degenerative mitral valve disease: Barlow’s disease and fibroelastic deficiency. *Semin Thorac Cardiovasc Surg*; 19(2): 90-6).

2. Evidence of sub-optimal fluid management (e.g., lack of diuretics, weight in excess of dry weight) in the opinion of the cardiology investigator
3. Structural / organic TV disease
4. Severe TR as determined by preoperative transthoracic echocardiography (TTE)
5. Implanted pacemaker or defibrillator, where the leads cross the TV from the right atrium into the right ventricle

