The KCCQ, SF-12, and EQ-5D Questionnaires will be completed by the patient to assess QOL. Data regarding completeness of QOL data collection and reasons for missing responses to questionnaires will be collected on the QOL Case Report Form.

Vital Status Check

At 36, 48 and 60 months (\pm 60 days) post randomization

The patient's vital status will be collected via telephone or a review of medical records.

Cost

Direct costing data for all randomized patients (from US sites) will be obtained by the DCC at the conclusion of the trial.

Event Driven Data Collection

Follow-Up Surgical Procedures

Event Driven

All operations following the initial study defined surgical intervention must be reported on the surgical procedure form within 48 hours of the knowledge of the event. If the operation is to address a complication, the coordinator must also complete an AE report. All intra-operative transfusion requirements must be documented. All follow-up surgical procedures will be recorded through month 24.

Adverse Events

Event Driven

Detailed information regarding AEs will be recorded at the time an AE occurs.

Investigators will be asked to make a judgment as to the seriousness and relationship of the event to the surgical intervention. All AEs will be recorded through month 24.

Re-Hospitalizations

Event driven

All ED visits (of any duration) and re-hospitalizations (>24 hours for any reason) must be reported on the Re-Hospitalization Form. This form collects limited information about hospital procedures, LOS, days in ICU, and discharge if applicable, as well as patient condition and disposition for each hospitalization. All re-hospitalizations will be recorded through month 24.

Outpatient Intervention

Event driven within 48 hours of knowledge of event

All outpatient procedures following the index hospitalization must be reported on the surgical procedure form within 48 hours of the knowledge of the event. If the intervention is to address a complication, the coordinator must also complete an AE report. All outpatient interventions will be recorded through month 24.

Missed Visit Assessment

Event Driven

If a patient is unable to return for follow-up before the closure of a study visit window, a missed visit assessment that captures the reason for missing the visit must be recorded on the protocol deviation form.

Mortality

Event Driven within 24 hours of knowledge of event

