Six Minute Walk and Gait Speed Tests: Differences between groups in gait speed and the distances travelled during the 6MWT will be compared using the Wilcoxon Rank-Sum test. We will also assess the extent to which changes over time (in gait speed and distance walked) are related to other outcomes.

Additional echo parameters: RV function (normal, mildly impaired, moderately impaired, severely impaired, peak tricuspid annular velocity, TAPSE, RVFAC) at 12 and 24 months and pulmonary artery pressure at 12 and 24 months will be compared between groups. RV volume as assessed by 3D TTE at 12 and 24 months will be compared between groups. Continuous variables will be compared for between group differences using the Wilcoxon Rank Sum test, and the level of function by chi-squared test.

Quality of life: QOL will be measured using the KCCQ, SF-12, and EQ-5D. We will employ two approaches to the analysis of QOL. The first will be to base the analysis on longitudinal mixed effects models. These models would predict outcome from treatment group and time. The mixed modeling approach requires an assumption that patient dropout is ignorable in that the probability of dropping out at any time is related only to previously observed data. Of course, this assumption may not hold, and moreover it is

impossible to test robustly from the data at hand. An alternative approach we will also use, not subject to this criticism, will be to separate the data into strata defined by the time of death or dropout. We will then estimate a separate linear model, including a treatment effect, for the data in each stratum. This method, known as pattern-mixture modeling, is not sensitive to un-testable assumptions about the dropout mechanism because it models the data directly in strata defined by dropout time. The method of Wu and Bailey is an instance of pattern-mixture modeling.

Adverse Events: Differences in the incidence of individual AEs within 24 months post-randomization will be compared between randomization arms using Poisson regression. Ninety-five percent confidence intervals (based on the Poisson distribution) for the risk ratios for individual AEs for treatment with MVS and TV annuloplasty versus MVS alone will be computed.

NYHA classification: The distribution of NYHA at 12 and 24 months will be presented for each randomization arm and compared using a chi-squared test.

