2.2 Secondary Objectives

Secondary aims of this trial include assessment of the impact of these two surgical approaches on right heart performance and function, mortality, adverse events (AEs), quality of life (QOL), functional status, presence and severity of TR, and health resource use.

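### SAP 6.5.2.5 limits its adverse event comparison to serious events plus two named ones: narrower than the protocol's analysis section, and at odds with its own next sentence

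*SAP*

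**What the plan says.** The Adverse Events paragraph of the protocol (Analytical Plan, Analyses of Secondary Endpoints) reads: "Differences in the incidence of individual AEs within 24 months post-randomization will be compared between randomization arms using Poisson regression". It goes on to promise 95% intervals for individual AEs, and neither sentence mentions seriousness.

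SAP 6.5.2.5 keeps the Poisson regression and the 24 months. Its first sentence, however, sets the comparison as "Differences in the rate of individual serious AEs, AV-Block requiring pacemaker implantation, and new-onset atrial fibrillation within 24 months post-randomization". The next sentence begins "Ninety-five percent confidence intervals for the rate ratios for individual AEs", without the word *serious*.

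The endpoint lists are the same in both documents (Protocol, Endpoints; SAP 5.2.5). The first item is "Frequency of SAEs", followed by AV block needing a pacemaker and new-onset atrial fibrillation. The secondary objectives are wider. In both documents they run to "right heart performance and function, mortality, adverse events (AEs), quality of life (QOL") and beyond, naming adverse events without a seriousness limit.

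On collection, the protocol says "All AEs will be recorded through month 24". Its section on the Event Adjudication Committee (EAC) has that committee adjudicate all AEs from source documents.

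**The concern.** The two documents give different scopes for one safety comparison, and the SAP gives two scopes in consecutive sentences. Two programmers could build different tables from SAP 6.5.2.5, and each could defend the choice.

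The trial asks whether adding a tricuspid procedure to mitral surgery is safe as well as effective, so complications short of serious are part of the question. The protocol went out of its way to capture one of them. Its revision history records that the pleural effusion definition was widened to include medical management so that fluid management could be analysed. Read literally, the first sentence of SAP 6.5.2.5 omits the non-serious effusions which that change brought in.

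The SAP's statement of purpose adds a second consequence: analyses that it does not explicitly identify are to be labelled post hoc or unplanned. The comparison of all individual AEs in the protocol's analysis section could therefore be published as unplanned.

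**Working it through.** The documents state no figure on this point, so the main check sets the texts side by side.

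**1. Scope of each text**

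| Place | Scope |
|---|---|
| Protocol, secondary objectives; SAP 2.2 | adverse events |
| Protocol, Endpoints; SAP 5.2.5 | SAEs, AV block with pacemaker, new-onset AF |
| Protocol, Analytical Plan, Adverse Events | individual AEs |
| SAP 6.5.2.5, first sentence | individual serious AEs, AV block with pacemaker, new-onset AF |
| SAP 6.5.2.5, second sentence | individual AEs |

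The SAP's test matches the endpoint lists. It is narrower than the protocol's analysis section and than its own interval sentence.

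**2. Is the gap covered elsewhere in the SAP?** No. Section 6.5.2.1 covers MACCE, whose non-fatal parts are stroke and serious heart failure. Section 6.5.2.6 counts readmissions, not event types. No other section compares non-serious AEs.

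**3. Which protocol-defined events can fall into the gap?** From Specific Adverse Event Definitions:

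- *Pleural effusion* can qualify on medical management such as diuresis, with no drainage.
- *Localized infection* can qualify on non-prophylactic antimicrobial treatment, so some cases need not be serious.
- *Permanent pacemaker*: the category takes in sustained bradycardia as well as conduction abnormalities, and counts every pacemaker whether or not it accompanies a serious AE. The SAP's named exception covers AV block only, so a non-serious pacemaker for sustained bradycardia is outside it.

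Other types are unlikely to be affected. Pericardial collection requires surgery or catheter drainage, renal failure requires new dialysis, and dehiscence requires surgical repair. New-onset AF is kept by name.

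**4. What the restriction could cost in precision (illustration only).** The documents give 400 patients randomized 1:1, that is 200 per arm. Assumed: 0.2 events of one type per control patient over 24 months, a true rate ratio of 1.5, and the same rate ratio for serious and for all events. The serious share f is varied.

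- Events: e0 = 200 × 0.2 × f; e1 = 1.5 × e0.
- SE(log RR) = √(1/e0 + 1/e1); 95% interval = 1.5 × exp(±1.96 × SE).
- Power ≈ Φ(ln 1.5 / SE − 1.96).
- Widening of the log-scale interval relative to all events = 1/√f.

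| f | Events, control vs annuloplasty | 95% interval | Power | Widening |
|---|---|---|---|---|
| 100% | 40 vs 60 | 1.01 to 2.24 | 51% | 1.00 |
| 75% | 30 vs 45 | 0.95 to 2.38 | 41% | 1.15 |
| 50% | 20 vs 30 | 0.85 to 2.64 | 29% | 1.41 |
| 25% | 10 vs 15 | 0.67 to 3.34 | 17% | 2.00 |

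Moving the control rate across 0.1 to 0.3 gives a power of 29% to 68% for all events and 17% to 41% if half are serious. The widening factor depends only on f.

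**The case against.** **The SAP follows the endpoint list.** Both lists name the same three items, and SAP 6.5.2.5 analyses exactly those. This stands: the mismatch is partly internal to the protocol. A reader might infer that the SAP abandoned the protocol's safety endpoint, and it did not. That explains the SAP's wording but does not reconcile it with the protocol's analysis section.

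**The narrowing is ambiguous.** The second sentence of SAP 6.5.2.5 can be read as covering all individual AEs. This also stands. A reader might infer that non-serious events are definitely excluded, but the documents support only that their comparison is not clearly planned.

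**Few events may be lost.** Many definitions already require an intervention, and the catch-all category is worded for other SAEs, which suggests that most listed events were conceived as serious. This stands as a limit on size. It does not remove the three examples above.

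**Does an unblinded judgment decide what is counted?** A reader might infer so, since "Investigators will be asked to make a judgment as to the seriousness and relationship of the event to the surgical intervention" and "Neither patients nor investigators will be blinded to treatment assignment due to the nature of the treatment intervention". If inclusion did turn on that call and the serious share were 50% in control and 40% or 60% with annuloplasty (assumed), a true rate ratio of 1.0 would appear as 1.0 × 0.40/0.50 = 0.8 or 1.0 × 0.60/0.50 = 1.2. The documents do not establish the premise. The EAC adjudicates all AEs, and nothing says whether it rules on seriousness or is masked to arm. The protocol also refers to a separate AE reporting and adjudication guidance that is not among these documents. Counting non-serious events would not remove open-label influence either, because recognizing an effusion and choosing to treat it are decisions made at the same unblinded sites.

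**Conclusion.** The inconsistency is real and should be resolved before data lock. The protocol's analysis section covers individual AEs of any seriousness. The test in SAP 6.5.2.5 covers serious AEs plus two named events, and its interval sentence is worded for individual AEs. Effusions managed by diuresis, some localized infections and non-serious pacemakers for sustained bradycardia are left without a clearly planned comparison, although the data are collected and adjudicated.

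The size cannot be derived. The documents give neither event rates nor serious shares, so the table only illustrates how precision falls with the serious share of one event type. It also assumes a common rate ratio for serious and all events, which need not hold, and it implies no loss for types that are nearly always serious. No bias in a particular direction can be claimed. The primary analysis is untouched.

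**What to change.** Keep what SAP 6.5.2.5 already has: Poisson regression, rate ratios with 95% intervals, the 24-month period, serious AEs, AV block requiring a pacemaker and new-onset AF. Extend it to every protocol-defined event type, so that both sentences agree with the protocol's analysis section. Suggested text:

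*Over the 24 months after randomization, Poisson regression will compare the arms on (i) each adverse event type defined in the protocol, counting serious and non-serious events together; (ii) the serious events of each type, shown separately; and (iii) AV block requiring a pacemaker and new-onset atrial fibrillation. Each comparison will be reported as a rate ratio with its 95% confidence interval.*

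It would also help to add one sentence saying whether the EAC rules on seriousness and is masked to arm.

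The cost is a short SAP revision, which the SAP allows before data lock, and extra table rows. No new data are needed. The downside is a longer safety table with more unadjusted comparisons, to be read as descriptive.
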